**4.4. Step 4 (Visits 7 – 13) – 1st Series of 10 Doses of VOR with 2 Infusions of HXTCs.**

Successful manufacturing of HXTc cells and acceptable clinical findings during the pre-dose safety assessment at Step 3, Visit 6 determine advancement to Step 4.

Participants receive 10 doses of VOR 400 mg PO every 72 hours. At study Visits 7 and 10, approximately 6 hours after their VOR dose, they will receive an HXTc infusion of up to  $1 \times 10^8$  cells/m^2. Thus, each participant receives ten VOR 400 mg doses and two HXTc infusions (HXTc #1 and #2) in Step 4.

**4.5. Step 5 (Visits 14 – 20) - 2nd Series of 10 Doses of VOR with 3 Infusions of HXTCs.**

Approximately 4 – 5 weeks after the 10th dose of VOR 400 mg (Visit 12), if participants meet the pre-dose safety assessment requirements at Step 4, Visit 13, participants return for their first Step 5 visit (Visit 14).

Participants receive 10 doses of VOR 400 mg PO every 72 hours (total VOR dose #11 – 20). At Visits 14, 16, and 19, participants receive HXTc infusions of up to  $1 \times 10^8$  cells/m^2 each (HXTc #3, #4, and #5). The first 2 HXTc infusions occur approximately 6 hours after their VOR dose; however, the last HXTc infusion (HXTc #5) will occur 1 – 3 days after the last VOR 400 mg dose (Dose #20).

If there are insufficient cells manufactured to allow five HXTc infusions at  $1 \times 10^8$  cell/m^2 each, the study team will review the amount of cells manufactured and change the HXTc dose to be less than  $1 \times 10^8$  cells/m^2 but  $\geq 5 \times 10^7$  cells/m^2 each.

Monitoring for toxicity occurs throughout Steps 4 and 5.

[figure not shown]
#### 4.6. Step 6 (Visits 21, 23, 24) – Immune Monitoring and Leuk #2

Following the final HXTC infusion, participants move into Step 6 for a minimum of three additional visits. The 2nd leukapheresis will occur at Visit 23 (Week 16), approximately 5 weeks after the last HXTC infusion to evaluate the effect of study treatment on the IUPM by QVOA.

All participants who receive greater than 8 doses of VOR (3200 mg) will be required to enter a study cancer registry where they will be contacted once a year for 5 years after completion of their study participation. The registry was created to monitor participants for the development of future malignancies given concern for genotoxic impact with the use of VOR.

NOTE: THE PROTOCOL AMENDMENT FOR VERSION 4.0 DATED 31 JANUARY 2022 ELIMINATED VISITS 22, 25, AND 26 FROM STEP 6 OF THE PROTOCOL.

#### 4.7. Figure 1: Study Schema

### 5. STUDY ENROLLMENT AND WITHDRAWAL

#### 5.1. Participant Inclusion Criteria

5.1.1. ≥ 18 years and < 65 years of age at screening

5.1.2. Ability and willingness of participant to give written informed consent.

NOTE: Due to the lack of foreseeable benefit to study volunteers, the study will not enroll illiterate or mentally incompetent volunteers.

5.1.3. Confirmation of HIV-1 infection

HIV infection is defined as documentation by any licensed rapid HIV test or HIV enzyme or chemiluminescence immunoassay (E/CIA) test kit at any time prior to study entry and confirmed by a licensed Western blot or a second antibody test by a method other than the initial rapid HIV and/or E/CIA, or by HIV-1 antigen, plasma HIV-1 RNA viral load.

NOTE: The term “licensed” refers to a US FDA-approved kit.

WHO (World Health Organization) and CDC (Centers for Disease Control and Prevention) guidelines mandate that confirmation of the initial test result must use a test that is different from the one used for the initial assessment. A reactive initial rapid test should be confirmed by either another type of rapid assay or an E/CIA that is based on a different antigen preparation and/or different test principle (e.g., indirect versus competitive), or a Western blot or a plasma HIV-1 RNA viral load.

5.1.4. On antiretroviral therapy for at least 24 months and on potent antiretroviral therapy for  $\geq 6$  months prior to Screening (Visit 1).

Potent ART is defined by current treatment guidelines and consists of at least nucleoside/nucleotide reverse transcriptase inhibitors plus a non-nucleoside reverse transcriptase inhibitor, integrase inhibitor, or a protease inhibitor without interruption (defined as missing more than 9 total days in the 12 weeks prior to Screening).

Other potent fully suppressive antiretroviral combinations will be considered on a case-by-case basis. Prior changes in or elimination of medications for easier dosing schedule, intolerance, toxicity, or other reasons are permitted if an alternative suppressive regimen was maintained.

5.1.5. Ability and willingness of participant to continue ART throughout the study.

5.1.6. Able and willing to adhere to protocol therapy, schedule, and judged adherent to antiretroviral therapy (adherence defined in 5.1.4.)

5.1.7. Plasma HIV-1 RNA  $< 50$  copies/mL at two time points in the previous 12 months prior to study screening (one time point can be at screening) and never  $\geq 50$  copies/mL on two consecutive time points in the last 24 months.

NOTE: A single unconfirmed plasma HIV RNA  $\geq 50$  copies/mL but  $< 1000$  c/mL is allowed if a subsequent assay was  $< 50$  copies/mL; but none in the 6 months preceding the study screening visit.

5.1.8. Plasma HIV-1 RNA  $< 50$  copies/mL at screening.

5.1.9. CD4+ cell count  $\geq 350$  cells/mm^3 at screening.

5.1.10. No active HCV infection at or within 90 days of screening.

*Note: NO active HCV defined as negative HCVAb or if HCVAb is positive, reflex HCV RNA is negative.*

5.1.11. No active HBV infection (measurable HBV DNA or HBsAg+) at or within 90 days of screening.

5.1.12. Women with written documentation of any of the following:

- prior hysterectomy OR bilateral oophorectomy (removal of both ovaries)
- bilateral tubal ligation or non-surgical permanent sterilization
- Women with intact uterus and ovaries who have not had a period for  $\geq$  one year AND have a documented FSH level indicating postmenopausal status.

5.1.13. All male study volunteers must agree not to participate in a conception process (e.g. active attempt to impregnate, sperm donation, in vitro fertilization) and, if participating in sexual activity that could lead to pregnancy, the male study volunteer and his female partner must use two reliable methods of contraception (condoms, with or without a spermicidal agent; a diaphragm or cervical cap with spermicide; an IUD; or hormonal-based contraception) simultaneously while receiving the protocol-specified study products and for 6 weeks after stopping the study products. Participants must use a reliable barrier method of contraception (condom, cervical cap) along with another form of contraception.

NOTE: For female partners receiving ritonavir, estrogen-based contraceptives are not reliable and an alternative method should be suggested.

5.1.14. Ability and willingness to provide adequate locator information.

5.1.15. Ability and willingness to communicate effectively with study personnel.

5.1.16. Adequate vascular access for HXTC infusion and leukapheresis.

5.1.17. Able to swallow pills without difficulty.

5.1.18. Potential participant must have adequate organ function as indicated by the following laboratory values:

System	Laboratory Value
Hematological	
Absolute neutrophil count (ANC)	$\geq 1,500 / \text{mcL}$
Platelets	$\geq 125,000 / \text{mcL}$
Hemoglobin	$\geq 12 \text{ g/dL}$ (male) and $\geq 11.0 \text{ g/dL}$ (females)
System	Laboratory Value
Coagulation	
Prothrombin Time (PT) or INR	$< 1.1 \times \text{ULN}$
Chemistry	

K+ levels	WNL
Mg++ levels	WNL
Glucose	Screening serum glucose ≤ Grade 1 (fasting or non- fasting)
Albumin	≥ 3.5 g/dL or ≥ LLN
Renal	
Creatinine clearance determined by the CKD-Epi equation found at: https://www.qxmd.com/calculate/calculator_251/egfr-using-ckd-epi	eGFR > 60mL/min
Hepatic	
Serum total bilirubin	Total bilirubin < 1.1 times the ULN range. If total bilirubin is elevated, direct bilirubin must be < 2 times the ULN range.  NOTE: If participant is on an atazanavir-containing therapy, then a direct bilirubin should be measured instead of the total bilirubin and must be ≤ 1.0 mg/dL.
AST (SGOT) and ALT (SGPT)	< 1.25 X ULN
Alkaline Phosphatase	< 1.25 X ULN
Lipase	< 1.1 X ULN

 LLN for Mg++ per the clinical laboratory's normal range used for this study is a grade 1 event per DAIDS Toxicity Table and is allowed for eligibility

ULN = upper limit of normal    LLN = lower limit of normal    WNL = within normal limits

## 5.2. **Participant Exclusion Criteria**

- 5.2.1. Known allergy or sensitivity to components of VOR and its analog or to components in the HXTC product.
- 5.2.2. Women without written documentation of menopause (absence of a period for ≥ one year and FSH level indicating menopause), hysterectomy or bilateral oophorectomy, non-surgical permanent sterilization, or bilateral tubal ligation.
- 5.2.3. Untreated syphilis infection (defined as a positive rapid plasma reagin (RPR) without clear documentation of treatment).

*Note: In cases of untreated syphilis, participant may re-screen following documentation of adequate treatment of syphilis*

- 5.2.4. All male participants expecting to father children within the projected duration of the study.

- 5.2.5. Receipt of compounds with HDAC inhibitor-like activity, such as valproic acid within 30 days prior to screening.
- 5.2.6. Use of any investigational antiretroviral agents within 30 days prior to screening.
- 5.2.7. If the study PI (or designee) is unable to construct a fully active alternative ART regimen based on previous resistance testing and/or treatment history.
- 5.2.8. Use of the following medications that carry risk of torsade des pointes: amiodarone, arsenic trioxide, astemizole, bepridil, chloroquine, chlorpromazine, cisapride, clarithromycin, diopyramide, dofetilide, domperidone, droperidol, erythromycin, halofantrine, haloperidol, ibutilide, levomethadyl, mesoridazine, methadone, pentamidine, pimozidine, probucol, procainamide, quinidine, sotalol, sparfloxacin, terfenadine, thioridazine.
- 5.2.9. Use of any of the following within 90 days prior to screening: immunomodulatory, cytokine, or growth stimulating factors such as systemic corticosteroids, cyclosporine, methotrexate, azathioprine, anti-CD25 antibody, IFN, interleukin-2 (IL-2), coumadin, warfarin, or other Coumadin derivative anticoagulants.
- 5.2.10. Prior use of any HIV immunotherapy or HIV vaccine within 6 months prior to Screening, except for prior HXTc infusions.
- 5.2.11. Received any infusion blood product, immune globulin, or hematopoietic growth factors within 90 days prior to study screening.
- 5.2.12. Pregnancy or breast-feeding.
- 5.2.13. History or other clinical evidence of severe illness, malignancy, immunodeficiency other than HIV, or any other condition that would make the participant unsuitable for the study in the opinion of the investigator (or designee).
- 5.2.14. Use of topical steroids over a total area exceeding 15 cm^2 within 30 days prior to Screening.
- 5.2.15. Treatment for an active AIDS-defining opportunistic infection within 90 days prior to Screening.
- 5.2.16. Any active malignancy that may require chemotherapy or radiation therapy.
- 5.2.17. Compulsorily detained (involuntarily incarcerated) for treatment of either a psychiatric illness or a physical illness, e.g., infectious disease. Prisoner recruitment and participation is not permitted.

5.2.18. Known psychiatric or substance abuse disorders that would interfere with participant's ability to fully cooperate with the requirements of the trial as assessed by the study investigator (or designee).

5.2.19. History or other clinical evidence, as assessed by the study PI (or designee), of significant or unstable cardiac disease (e.g., angina, congestive heart failure, recent myocardial infarction, significant arrhythmia requiring medical or surgical therapy) or clinically significant electrocardiogram (ECG) abnormalities.

5.2.20. Participation in another investigational clinical research study (with the exception of an antiretroviral treatment trial that uses FDA approved antiretroviral agents) or use of investigational agents within 30 days prior to screening.

NOTE: Co-enrollment in observational only studies is permitted.

NOTE: Co-enrollment in the ACTG 5332 REPRIEVE study (NCT023442900) and using FDA approved pitavastatin is permitted provided participant enrolled on ACTG 5332 and has taken the study provided medication  $\geq$  4 months.

### **5.3 Strategies for Recruitment and Retention**

There are several venues for recruitment available to the study team:

In the UNC ID clinic and/or other local HIV clinics, there is a large pool of patients with long-term viral suppression on ART interested in participating in research. Many have previously participated in clinical research studies in the past. These individuals will be provided with the opportunity to discuss this study with their provider and the study coordinator.

The UNC acute HIV program actively enrolls persons diagnosed with AHI into treatment protocols and also follows persons off treatment studies in a longitudinal cohort protocol. Currently there are at least 65 active participants who were seen and treated in AHI in the UNC cohort.

Individuals who have signed the UNC CFAR (Center for AIDS Research) database consent as well as those who have signed the consent for the PHI (Primary HIV Infection) studies/database will be identified and approached about the study by either their primary care provider or the study coordinator, after consultation with their primary care provider.

If individuals are interested in participating in the study, they will be provided with appropriate study information and the opportunity to screen. All potential participants will be informed that on rare occasions some of the serious side effects described in this protocol as well as other unpredicted adverse events can occur. They will be told that

their participation in this study will allow researchers the opportunity to collect valuable information about the use of HXT in individuals with durable viral suppression and its ability to improve immune responses. Potential participants will be informed that there may be no direct and immediate benefits to them as volunteers in this study, but information learned from this study may be of value to the participant and other people with HIV disease.

Participants will be screened and recruited in the Infectious Diseases (ID) Clinic and the Clinical and Translational Research Center (CTRC) of the University of North Carolina (UNC) at Chapel Hill. Study activities can take place in the CTRC unit, the Apheresis Lab, the American Red Cross (ARC) in Durham, NC, and/or the UNC ID Clinic, located in the University of North Carolina Memorial Hospital.

Screening will take place in a step-wise manner. Screening procedures and assessments will include the following: completion of informed consent process, determination of HIV infection status, documentation of stable ART and HIV RNA < 50 copies for  $\geq 2$  years, locator information, and screening safety laboratory testing and safety procedures.

Screening and enrollment occur in Step 1. After establishment of the baseline safety (Visit 1) parameters and qualifying for the study per the Inclusion and Exclusion Criteria, the participant is enrolled (Visit 2) and completes the baseline leukapheresis. The IUPM measurement of  $\geq 0.3$  obtained from samples collected during the baseline leukapheresis determine whether the participant moves to Step 3.

#### **5.4. Participant Withdrawal**

##### Handling of Participant Withdrawals or Participant Discontinuation of Study Intervention

Participants failing to meet criteria to advance to Step 4 are not required to complete an end of study visit (Step 6, Visit 23). Reasons for not progressing to Step 4 include:

- Inability to manufacture HXT product in Step 3
- Failure to meet requirements established for the pre-dose safety assessment for Step 4 at Visit 6.

If the participant withdraws, discontinues, or fails to advance in the study for any reason after initiating VOR dosing and HXT infusions in Step 4, the participant would be asked to complete an Early Discontinuation Study Visit (Step 6, Visit 23). This visit will occur  $\geq 4$  weeks but  $\leq 8$  weeks after the last documented visit or study treatment, whichever occurred last. Participants would then proceed to complete Visit 24.

In scenarios where participants are discontinued or withdrawn after receiving VOR doses in combinations with HXT infusions, the study PI (or designee) will make every effort to complete the Early Discontinuation Study Visit/End of Study Intervention (Step 6, Visit 23) evaluations.

The Early Discontinuation or End of Study Interventions Visit will include the clinical assessments and required labs per the SOE. The completion of the Leukapheresis procedure at this visit will be determined on a case-by-case basis by the study PI (or designee).

UNC reserves the right to discontinue the study for any reason at any time. The study may also be stopped if, in the opinion of the principal investigator and/or protocol team, the continuation of the study represents an unwarranted medical risk to the participants.

## **5.5. Premature Termination or Suspension of Study**

### **5.5.1. Study Treatment Stopping Rules or Permanent Treatment Discontinuation**

A participant will not receive VOR and/or HXTc infusions if any of the following occurs:

- Pregnancy of study participant
- Treatment related  $\geq$  Grade 3 adverse event
- Requirement for prohibited concomitant medications
- Inability to complete treatments as defined in the protocol
- Request by participant to terminate study treatments
- Clinical reasons believed life-threatening by the PI or designee
- Hematologic dose-limiting toxicity defined as any confirmed toxicity  $\geq$  Grade 2, that cannot clearly be attributed to another reversible cause other than VOR
- Development of a dose-limiting toxicity
- HIV RNA  $> 150$  copies/mL on two consecutive determinations.

Participants who prematurely discontinue study treatment will move to Step 6, Visit 23 and will be followed through Visit 24. See section 5.4, Participant Withdrawal, for details on study procedures to be completed.

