**7.3.3.7. Visit 13 - Safety Follow-Up and Step 5 Pre-Dose Safety Assessment**

Occurs between 7 and 14 days after Visit 12 and within 21 days of Step 5, Visit 14.

The pre-dose safety labs must be reviewed and signed off by the study PI or designee prior to Visit 14. If the participant does not meet one or more of the requirements of the pre-dose safety lab assessments, repeat of the abnormal lab/s can occur one time only.

After repeat testing, any lab values that remain outside the guidelines listed below but are considered clinically non-significant and documented as such by the study PI (or designee), may proceed to the dosing/infusion visit after review and approval of the case by the protocol and/or safety committee.

Please reference the SOE for clinical and research procedures done at this visit.

Hematology	Laboratory Value
ANC	$\geq 1,500 / \text{mcL}$
Platelets	$\geq 125,000 / \text{mcL}$
Hemoglobin	$\geq 12 \text{ g/dL}$ (male) and $\geq 11.0 \text{ g/dL}$ (females)
Chemistry	
K + levels	WNL
Mg ++ levels	WNL
Glucose	$\leq$ Grade 1 (fasting or non- fasting)
Renal	
Creatinine	$< 1.3 \times \text{ULN}$
Hepatic	
Total bilirubin	$< 1.6$ times the ULN range. If total bilirubin is elevated, direct bilirubin must be $< 2$ times the ULN range.
AST (SGOT) and ALT (SGPT)	$\leq 2.5 \times \text{ULN}$
Alkaline Phosphatase	$\leq 2.5 \times \text{ULN}$
Other Testing	
Serum pregnancy test (all females)	Negative
RPR	No active infection
HIV RNA	$< 50$ copies

CD4	$\geq 350$
-----	------------

Estimated Blood Volume: up to 60 mL

Participants will be given 1 dose of VOR 400 mg to take home. Upon verification of acceptable labs, participants will be contacted to verify date and time of Visit 14 and also to verify the time participant is to take the 11th dose of VOR that morning. Plans will be made for participants to return the dose of VOR 400 mg to the study coordinator should the participant fail to have acceptable pre-dose labs for Step 5.

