#### 7.3.4. Step 5 (Visits 14 – 20) Second Series of VOR 400 mg x 10 doses and three HXTC Infusions

Participants with acceptable pre-dose safety labs as determined in Visit 13 are eligible to start dosing with VOR and receive their 3rd HXTC infusion in Step 5, Visit 14.

#### Visit Windows for Step 5

Visit #	Visit Evaluations	Visit Window
Visit 14	VOR Dose #11 and HXTC Infusion #3	$\leq 21$ days after Visit 13
Visit 15	Safety check and Research Labs	1 - 3 days after Visit 14
	VOR Dose #12	3 days after Visit 14 (Dose 11 + 3 days)
	VOR Dose #13	6 days after Visit 14 (Dose 11 + 6 days)
	VOR Dose #14	9 days after Visit 14 (Dose 11 + 9 days)
	VOR Dose #15	12 days after Visit 14 (Dose 11 + 12 days)
Visit 16	VOR Dose #16 and HXTC Infusion #4	15 days after Visit 14 (Dose 11 + 15 days)
Visit 17	Safety Check and Research Lab	1 - 3 days after Visit 16
	VOR Dose #17	3 days after Visit 16 (Dose 11 + 18 days)
	VOR Dose #18	6 days after Visit 16 (Dose 11 + 21 days)
	VOR Dose #19	9 days after Visit 16 (Dose 11 + 24 days)
Visit 18	VOR Dose #20	12 days after Visit 16 (Dose 11 + 27 days)
Visit 19	HXTC Infusion #5	1-3 days after Visit 18
Visit 20	Safety Check and Research Lab	1-3 days after Visit 19

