##### 7.3.4.1.4. Post Infusion

Provide participant with doses #12 – #16 of VOR 400 mg to take home.

The study coordinator will contact participants via their preferred way of communication approximately 2 to 3 days after study product administration to inquire about any reactions or potential TEAEs. Instruct the participant to contact the study coordinator or investigator if such any adverse events occur after this infusion or at any point during the study. The study coordinator can combine this assessment with VOR dosing reminder when these events overlap.

7.3.4.2. **Visit 15 – Safety Follow-Up Visit**

The study participant will have a post HXTC infusion follow-up visit per SOE with labs drawn 1 – 3 days post infusion.

Estimated Blood Volume: up to 55 mL

7.3.4.3. **Visit 16 - Dose #6 of VOR and 4th HXTC Infusion**

All female participants require a negative POC urine pregnancy test within 48 hours of infusion visit. If, despite the documentation of infertility, a female participant has a positive pregnancy test at this visit, they will be discontinued from the study and not receive the HXTC infusion or additional doses of VOR.

Estimated Total Blood Volume: up to 45 mL

7.3.4.3.1. **VORINOSTAT 400 mg**

Participants take VOR 400 mg PO the morning of this visit and document the time. This is the 6th dose in the series of 10 doses.

Reference section 7.3.3.1.1. for dosing time and process prior to infusion.

7.3.4.3.2. **Pre – HXTC Infusion**

Safety evaluations and research lab collection:

- Collect safety labs (STAT) or within 48 hours of the visit.
- Collect research labs on the day of visit only.
  - Collect approximately 4 hours after AM VOR dose. Collection can be +/- one hour of the 4-hour time point.

Documented PI review of clinical labs as well as review of clinical assessments done at this visit are required prior to the thawing and infusion of HXTC study product.

Administration of HXTC can be delayed up to 1 week, pending resolution of physical findings or lab abnormalities.

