#### 7.3.4.6.1. Pre – HXTc Infusion

Reference section 7.3.3.1.2. and SOE for visit procedures and processes.

Safety evaluations and research lab collection:

- Collect safety labs (STAT) or within 48 hours of the visit.
- Collect research labs on the day of visit only.

Documented PI review of clinical labs as well as review of clinical assessments done at Visit 18 as well clinical assessments from this visit are required prior to the thawing and infusion of HXTc study product.

Administration of HXTc can be delayed up to 1 week, pending resolution of physical findings or lab abnormalities.

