##### **8.1.2.3. Clinical Chemistry**

Assessments include Sodium (Na), potassium (K), chloride (Cl), bicarbonate (CO2), glucose, blood urea nitrogen (BUN), creatinine, calcium (Ca), magnesium (Mg), ALT, AST, alkaline phosphatase, total bilirubin.

In addition to the labs listed above, the following labs will be done at screening and Visit 23 only:

- Direct bilirubin will be obtained if participant is on atazanavir.
- Lipase, albumin, total protein, cholesterol, and triglycerides

8.1.2.4. **Hematology** – All assessments include CBC with WBC differential

8.1.2.5. **Safety Labs**

All participants will have safety labs (CBC with differential and chemistries) done at protocol required visits. Labs from the screening visit will be considered baseline. All lab values obtained pre- and post-dosing that are abnormal and meet grading standards per the DAIDS Table for Grading the Severity of Adult and Pediatric Adverse Events, version 2.1, July 2017 will be re-assessed based on these initial parameters.

Creatinine clearance calculations will use the CKD-EPI equation. This calculation can be found at

[https://www.qxmd.com/calculate/calculator\\_251/egfr-using-ckd-epi](https://www.qxmd.com/calculate/calculator_251/egfr-using-ckd-epi)

The creatinine clearance will be required for study enrollment eligibility. The study assesses serum creatinine level at all the safety lab checks and uses the serum creatinine value for toxicity grading and as confirmation to progress to each dosing Step. Grade the serum creatinine per the DAIDS Table for Grading the Severity of Adult and Pediatric Adverse Events, version 2.1, July 2017.

8.1.2.6. **Prothrombin time (PT), INR, and APTT** - at Screening Visit only.

8.1.2.7. **Follicle Stimulating Hormone (FSH) Test**

This test is done at screening to document menopause in women who have been without a period for > 12 months.

8.1.2.8. **HBsAg and Hep C Antibody** Both hepatitis tests must be negative or non-detected to be included on the study. A positive HCV AB test reflexed to Hepatitis C RNA revealing a negative result is acceptable.

8.1.2.9. **RPR**

If positive and participant has documentation of recent appropriate treatment, they may continue in study. Completion of RPR testing occurs again at Step 3, Visit 6 and Step 4, Visit 13.

8.1.2.10. **HIV-1 RNA**

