Review medical history (including new medical conditions)	X	X					X	X		X	X	X	
Assess Adverse Event	X	X					X	X		X	X	X	
Review ART & ART Adherence	X	X					X	X		X	X	X	
Review Concomitant Medication	X	X					X	X		X	X	X	
Phone Assessment	(T)		(T)	(T)	(T)	(T)	(T)		(T)	(T)	(T)	(T)	
Vorinostat Administration (400 mg) (home)	X		X	X	X	X	X		X	X	X	X	
CTL Infusion	X						X					X	
CTL Pre-medication	X						X					X	
Post infusion assessment	X	X					X					X	
Leukapheresis (& meal)													
Clinical Laboratory Procedures													
Chemistries		X 					X 				X 		
Coagulations (PT/INR/PTT)													
CBC with differential		X					X 			X			
Pregnancy Test or FSH Test													
CD4+ T Cell Differential Panel													
HIV-1 RNA PCR													
HBsAg & HCV Ab													
Donor ID Panel 													
RPR													
Urine Pregnancy – POCT 	X 						X 				X 		
Urinalysis													
Research Laboratory Procedures 													
Single Copy Assay		X											
PBMC - HDAC Responsive Gene Measurement	X	X					X 	X		X	X	X	
Single PK sample (VOR)							X						
Cells for CTL production													
HLA typing													
Immune Response, Viral Inhibition & Epitope Mapping													
Resting Cell Assay and CTL latency													

Step 6; Immune Monitoring						
Evaluations	IM Visit #1	IM Visit #2 Eliminated	IM Visit #3 & Leukapheresis #2	IM Visit #4	IM Visit #5 Eliminated	IM Visit #6 Eliminated
Time to Visit	~ 7 days after Visit 19		~ 4 weeks after Visit 19	~ 9 weeks after Visit 19		
Visit Windows	3 days (+/-)		1 week (+/-)	1 weeks (+/-)		
Study Week	13		16	21		
Study Visit	21	22	23	24	25	26
Clinical Procedures						
Consent, Eligibility, Demographics & Medical History						
Assignment of PID						
Assignment of SID						
Complete Physical Examination (vital signs & weight)			X			
Height						
Assess venous access						
Advancement Criteria						
Pre-Dose Clinical Assessment						
Targeted Clinical Assessment 	X			X		
Review medical history (including new medical conditions)	X		X	X		
Assess Adverse Event	X		X	X		
Review ART & ART Adherence	X		X	X		
Review Concomitant Medication	X		X	X		
Phone Assessment						
Vorinostat Administration (400 mg) (clinic)						
CTL Infusion						
CTL Pre-medication						
Post infusion assessment						
Leukapheresis (& meal)			X			
Clinical Laboratory Procedures						

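### No HIV-1 RNA PCR is scheduled in Step 5, so planned testing cannot trigger the viremia stopping rule during VOR doses 11–20 and HXTC infusions 3–5

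*Combined protocol and SAP*

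**What the plan says.** Section 5.5.1 opens its list of treatment-stopping conditions with "A participant will not receive VOR and/or HXTc infusions if any of the following occurs". One condition is HIV RNA above 150 "copies/mL on two consecutive determinations". Section 2.2.6 makes a related commitment: a value above 50 copies/mL is repeated, and confirmed viremia above 150 leads to discontinuation from the study.

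The provisions that decide when HIV RNA is measured around Step 5 are these:

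- **Visit 13 (7.3.3.7).** HIV RNA must be below 50 copies. One repeat of a failing value is allowed. A participant whose value is still outside the limits, but is documented as clinically non-significant, "may proceed to the dosing/infusion visit after review and approval of the case by the protocol and/or safety committee".
- **Visit 14 (7.3.4.1.2).** The laboratory review before infusion #3 uses the Visit 13 results.
- **Visit 16 (7.3.4.3.2).** The instruction is "Collect safety labs (STAT) or within 48 hours of the visit". Visit 19 (7.3.4.6.1) carries the same instruction.
- **Content of safety labs (8.1.2.5).** "All participants will have safety labs (CBC with differential and chemistries) done at protocol required visits". HIV RNA is not part of the set.
- **Single copy assay (8.1.3.3).** Plasma is stored and analyzed in batches.
- **Appendix A, Step 5.** The HIV-1 RNA PCR row is present and empty for Visits 14–20. The chemistry, CBC, urine pregnancy and single copy assay rows of the same table carry marks.
- **Appendix A, Step 6.** HIV-1 RNA PCR is marked at Visits 21, 23 and 24. Visit 21 is set at about "7 days after Visit 19", with a window of 3 days either way.

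**The concern.** A stopping rule that needs two consecutive results works only if results arrive while there is still treatment to stop. In Step 5 the schedule produces none. A participant who becomes viremic after Visit 13 could take all ten remaining VOR doses and receive all three remaining infusions, with every scheduled procedure done correctly and no result that could halt treatment.

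This matters for two reasons found in the protocol. Section 2.2.6 names the unmasking of latent HIV as a risk of this drug class. Section 2.3.1 accepts that infused HIV-specific CD4+ T cells may be lost to HIV infection and answers that participants are durably suppressed. No scheduled result confirms that suppression between Visit 13 and infusions #4 and #5. Section 10.5 also promises monthly monitoring of virologic failures, but this month of treatment generates no scheduled PCR data for that review.

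**Working it through.** **Inputs.** Dose and visit timing come from the Step 5 window table in 7.3.4 and from 4.5. The Visit 13 window comes from 7.3.3.7, the Visit 21 window from Appendix A, and the permitted delay of infusion #5 from 7.3.4.6.1 (it "can be delayed up to 1 week, pending resolution of physical findings or lab abnormalities").

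**The plan's own figure.** Doses 11 to 20 span nine 3-day intervals: 9 × 3 = 27 days. This matches the Step 5 table.

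**Step 5 timeline, with dose 11 (Visit 14) as day 0.**

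- Doses 12–20: days 3, 6, 9, 12, 15, 18, 21, 24, 27.
- Infusion #4 (Visit 16): day 15.
- Infusion #5 (Visit 19): 27 + (1 to 3) = day 28–30.
- Visit 21: infusion #5 + 7 ± 3 days, so 28 + 4 = 32 to 30 + 10 = 40. With the one-week delay of infusion #5, up to 47.

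**Scheduled PCRs from dose 11 to infusion #5:** 0. The rule needs 2.

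**Interval between scheduled PCRs, Visit 13 to Visit 21.** Visit 14 is 28–35 days after Visit 12. Visit 13 is 7–14 days after Visit 12 and no more than 21 days before Visit 14. Visit 13 to Visit 14 is therefore 14–21 days.

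- Shortest: 14 + 27 + 1 + 4 = 46 days.
- Longest: 21 + 27 + 3 + 10 = 61 days, or 68 with the one-week delay.
- Nominal: Week 6 to Week 13 = 7 weeks.

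**What an added PCR could stop.** The documents give no turnaround time. Assume T days per result, a repeat drawn 1 day after the first result, and a dose due on the confirmation day already taken. Confirmation then falls on draw day + 2T + 1.

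| Draw | T = 1 | T = 3 | T = 5 |
|---|---|---|---|
| Visit 15 (latest, day 3) | day 6: doses 14–20, infusions #4 and #5 | day 10: doses 15–20, infusions #4 and #5 | day 14: doses 16–20, infusions #4 and #5 |
| Visit 16 (day 15) | day 18: doses 18–20, infusion #5 | day 22: doses 19–20, infusion #5 | day 26: dose 20, infusion #5 |
| Visit 18 (day 27) | day 30: infusion #5 may already be given | day 34: too late on the usual schedule | day 38: too late on the usual schedule |

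Each cell gives the confirmation day and the treatment that could still be withheld. A Visit 16 draw leaves 13–15 days before infusion #5. A Visit 18 draw leaves 1–3 days, too short for two results.

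**The case against.** The strongest case against has four parts.

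**The table may be unreliable.** In the text reviewed, the Step 4 grid has lost all its marks and the Step 5 grid is somewhat distorted. Some research rows look shifted or lost: the immune response row is blank in Steps 5 and 6 although serial draws are promised. This is why nothing is claimed about Step 4, and why the Step 5 row should be compared with the original. The point does not rest on the grid alone, however. The neighboring clinical laboratory rows kept their marks, and the Step 5 visit text, read separately, names no HIV RNA test.

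**Visit 13 already gates Step 5.** It does, at a stricter limit than 150, and after the first ten doses and two infusions. Two values above 150 there would trigger the rule whatever committee approval was given. But it tests before dose 11 and cannot detect viremia that begins later.

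**The risk is low and other safeguards run.** Participants have long-term suppression and stay on ART. Section 2.2.6 reports rare blips and no drug resistance or ART failure. Adherence is reviewed at every visit, and continuation depends on it (8.1.1.12). The documents support no estimate of the probability of viremia, and no endpoint analysis is affected. All of this stands and bears on how serious the gap is. None of it gives the rule a scheduled trigger.

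**The fix recovers only part of the exposure.** This is correct. A Visit 16 draw alone saves one to three VOR doses and one infusion. A Visit 15 draw could save five to seven doses and two infusions, but only if viremia has begun by day 3.

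**Conclusion.** The concern holds. As written, scheduled testing cannot trigger the rule at more than 150 copies/mL during the second treatment series, which is 10 of 20 VOR doses and 3 of 5 HXTC infusions. The first scheduled PCR after Visit 13 comes 4–10 days after the last infusion.

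This rests on the empty Step 5 row being genuine, which the visit text supports. It concerns scheduled testing only: an unscheduled PCR could still trigger the rule, but the protocol specifies none, and the repeat in 2.2.6 applies only once a detectable value has been seen. The day counts come directly from the visit windows. The estimates of what an added test could withhold depend on the assumed turnaround of 1 to 5 days. The gap should be closed because it leaves a stated participant protection without a working trigger, not because viremia is shown to be likely.

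**What to change.** Mark HIV-1 RNA PCR, reported in real time, at Visit 16 ("15 days after Visit 14 (Dose 11 + 15 days"), where safety labs are already drawn on the day or up to 48 hours before. Preferably mark it at Visit 15 as well, where chemistry and CBC are already scheduled and an early signal leaves most of the series to withhold. State that any value above 50 copies/mL is repeated promptly, as 2.2.6 already intends, so that a confirmed value above 150 can stop the remaining doses and infusion #5. Do not rely on Visit 18. Check the original Step 4 schedule for an equivalent draw.

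The cost is one or two routine tests per participant, 12 × 1 = 12 to 12 × 2 = 24 in all, plus a schedule edit. The PCR tube volume is not stated, so check it against the visit limits (up to 55 mL at Visit 15, up to 45 mL at Visit 16). The drawback is an occasional repeat test for a transient blip. No threshold, dose or endpoint changes.
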